Subjects who prematurely discontinue study drug will require an immediate EOT assessment (either on the day of study drug discontinuation or as soon as possible following study drug discontinuation) and the SAE follow-up visit. Subjects that discontinue study drug early will continue in the study and be assessed with the off-treatment procedures at the subsequent visit(s) per the Schedule of Activities table, starting at the next scheduled visit from when study drug was permanently discontinued up to the final Week 12 visit. These off-treatment visits will include collection of SAEs, specific AEs of interest (ie, major adverse cardiac events [MACEs], acute pancreatitis, and possible cases of thyroid neoplasm), vital signs (including body weight), and concomitant medications. All subjects, except those who died, were lost to follow-up, or have a withdrawn consent, will have a follow-up visit at least 5 weeks after the last dose of study drug was taken to collect any SAEs and blood samples for PK and immunogenicity ADA assessments will be obtained.

The ERCQ is a home-based assessment in contrast to the IWQOL-Lite, PROMIS SF 10a, Patient Global Impression Status (PGIS), and Patient Global Impression of Change (PGIC), which are site-based assessments.

Subjects who withdraw from the study will not be replaced.

During the 12-week treatment phase (Day 1 to Week 12), subjects meeting protocol-specified glycemic rescue criteria will have rescue therapy initiated, and will remain in the study, continuing double-blind study drug. Rescue therapy may include increasing the dose of a current AHA or the initiation of a new AHA. Investigators will manage rescue therapy, including the selection of the specific AHA, its clinically appropriate initial dose and titration regimen (if applicable), the need to switch from one AHA rescue medication to another (ie, poor glycemic response to prior rescue medication), and be consistent with the labeled use within the country of the study site. Metformin, sulphonylureas, thiazolidinediones (TZDs), sodium-glucose cotransporter 2 (SGLT-2) inhibitors, dipeptidyl peptidase-4 (DPP-4) inhibitors, and insulin (basal only) are allowed as rescue medication; GLP-1 agonists and short-acting or intermediate insulins are not allowed as rescue medication.

The overall study duration is approximately 19 weeks and comprises of 3 phases:

- Pretreatment phase: 3 weeks comprised of:
 - Screening phase: 1 week

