**Table 2.1.1: Visit Windows**

Parameter	Scheduled Visit Number	Time Interval (label on output)	Time Interval (Day) a	Target Time Point (Day)
All	2	Baseline	≤1 b	1
	3	Week 2	1 c -28	15
	4	Week 6	29-64	43
	5	Week 12	65-105	85
	6	Post-Week 12	≥106	

a Relative to the day of the first dose of double-blind study medication.

b Up to the first dose of double-blind study medication.

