### 2.4. Study Day and Relative Day

“Study Day 1” or “Day 1” refers to the day of the first study agent administration on or after the randomization date. All efficacy and safety assessments at all visits will be assigned a day relative to this date.

Study day or relative day for a visit is defined as:

- Visit date - (date of Study Day 1) +1, if visit date is ≥ date of Day 1
- Visit date - Date of Day 1, if visit date < date of Day 1

There is no 'Day 0'.

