For summary statistics of serum JNJ-64565111 concentrations, concentration values below the lower limit of quantification will be treated as zero. Once a subject meets one of the following dosing deviation criteria, the subject's data will be excluded from the by-visit data analyses from that point onwards.

Dosing deviation criteria:

- Discontinued SC study agent administrations.
- Skipped a SC administration.
- Received an incomplete/ incorrect SC dose.
- Received an incorrect SC study agent.
- Received an additional SC dose.

In addition, if a subject has an administration more than 4 days earlier or later than the scheduled dosing date, the concentration data collected between such a dosing visit and the subsequent dosing visit will be excluded from the by-visit data analyses. For the Week 12 visit, if the PK sampling time deviates more than 4 days earlier or later than the scheduled date, the PK concentration at this visit will be excluded from the by-visit data analyses.

The conditions under which to exclude measurements from PK analysis:

- If date/time of Baseline sample is after date/time of first dose, then exclude the Baseline sample
- If Day 4 sample is  $>8$  days after 1st dose, then exclude the Day 4 sample
- If date of Week 2 sample – date of previous dose before date of Week 2 sample is  $< 3$  days or  $> 11$  days, then exclude Week 2 sample
- If date of Week 6 sample – date of previous dose before date of Week 6 sample is  $< 3$  days or  $> 11$  days, then exclude Week 6 sample

- If relative Study Day of Week 12 sample is < Day 80 or >Day 88 then exclude Week 12 sample
- If relative Study Day of Week 16 sample is < Day 108 or >Day 116 then exclude Week 16 sample
- If subject discontinues treatment early, then exclude the “Week 16” or “4 Week Follow-up” PK sample.

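### SAP 7.1 lists a Week 12 PK window (Study Days 80–88) one day earlier than its own ±4-day rule gives (Days 81–89), so valid Day 89 samples are lost; the Week 16 window appears to share the offset

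*SAP*

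**What the plan says.** SAP 7.1 contains two provisions on the timing of the Week 12 PK sample. The prose rule removes the Week 12 concentration from the by-visit analyses in the following case: "For the Week 12 visit, if the PK sampling time deviates more than 4 days earlier or later than the scheduled date". The list of conditions further down the same section, which governs exclusion from the PK analysis, says "If relative Study Day of Week 12 sample is < Day 80 or >Day 88 then exclude Week 12 sample". For the follow-up sample the list says "If relative Study Day of Week 16 sample is < Day 108 or >Day 116 then exclude Week 16 sample".

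The day scale is fixed elsewhere in the SAP. Section 2.4 defines the relative day on or after Day 1 as "Visit date - (date of Study Day 1) +1, if visit date is ≥ date of Day 1" and states that the scale has no Day 0. Table 2.1.1 counts its days as "Relative to the day of the first dose of double-blind study medication" and gives target days of 15, 43 and 85 for Weeks 2, 6 and 12. It has a Post-Week 12 row (Day 106 onward) but no target for Week 16.

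The timing of the follow-up visit is described in several ways. Protocol 4.1 says that subjects "will have a follow-up visit at least 5 weeks after the last dose of study drug was taken". Note c to the protocol's Schedule of Activities makes it approximately 5 weeks. SAP 1.2 gives 5 weeks after the last dose, and also a 4-week post-treatment phase.

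**The concern.** Two rules in one section give different Week 12 windows. A sample on Day 89 is four days after the target: the prose rule allows it and the list excludes it. A programmer who codes the list literally discards valid trough samples because of what looks like a counting slip.

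The Week 12 concentrations feed the by-visit tables, the steady-state plot, and the bar graph of weight loss and response rates by Week 12 concentration quartile. In a dose-ranging study meant to inform Phase 3 dose selection, those displays should not depend on which of two conflicting limits was coded.

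**Working it through.** **Inputs.** Study Day = date − date of Day 1 + 1, no Day 0 (SAP 2.4). Week 12 target = Day 85 (SAP Table 2.1.1). Week 12 tolerance = ±4 days (SAP 7.1, prose rule). Listed windows = Days 80–88 and 108–116 (SAP 7.1, list). Once-weekly dosing from Day 1 for 12 weeks (Protocol 6.1).

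**Reproducing the listed limits.** On the SAP's scale, week w falls on Day 7w + 1. This returns the table's own targets: 7×2+1 = 15, 7×6+1 = 43, 7×12+1 = 85. Leaving out the +1 gives centres of 7×12 = 84 and 7×16 = 112. Then 84 ± 4 = 80–88 and 112 ± 4 = 108–116, exactly the listed limits. A ±3-day tolerance around the correct centres gives 82–88 and 110–116, which does not match. Of the variants tried, only omission of the +1 reproduces the list.

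**Week 12 on the SAP's scale.** 85 ± 4 = Days 81–89.

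| Study Day | Days from target | Prose rule | List | Both applied |
|---|---|---|---|---|
| 80 | −5 | exclude | keep | exclude |
| 81–88 | −4 to +3 | keep | keep | keep |
| 89 | +4 | keep | exclude | exclude |

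**Cross-check.** For Weeks 2 and 6, SAP 7.1 keeps samples taken 3 to 11 days after the previous dose. The nominal 12th dose is on Day 1 + 11×7 = Day 78. Then 78 + 3 = 81 and 78 + 11 = 89, again Days 81–89. A Day 80 sample would be only 2 days after that dose.

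**Week 16.** Three nominal routes agree: 16×7 + 1 = 113; Week 12 plus the 4-week post-treatment phase, 85 + 28 = 113; nominal last dose plus 5 weeks, 78 + 35 = 113. The listed window has its midpoint at Day 112. If ±4 days around Day 113 is intended, the window is 109–117. That tolerance is borrowed from the general visit window in Protocol section 8, whose own sentence describes it both as 3 days and as ±4 days.

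**Size at Week 12.** The prose window holds 9 days (81–89) and the list removes one of them. If visits were spread evenly over ±4 days, 1/9 = 11% of in-window samples would be lost. With 3 × 47 = 141 subjects on active drug and a usable sample from every one, that is 141/9 = 15.7, about 16 subjects. Visits are scheduled to a target day, so the share at the +4 edge is probably well below 1 in 9.

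**The case against.** The best defence is that the list counts days elapsed since the first dose. On that count 80–88 is Study Days 81–89 and the conflict disappears. But the list is worded in relative Study Days, a term that SAP 2.4 defines with the +1, so the defence fails as the text stands. It does show how small the repair is.

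Several stronger readings are tempting and are not supported:

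- A reader might infer that the plan also keeps out-of-window Week 12 samples. That is true only of the list read alone. Both provisions are exclusions and nothing says the list overrides the prose, so a Day 80 sample is still removed from the by-visit analyses. With both applied, the consequence is the loss of Day 89.
- A reader might treat the Week 16 limits as equally proven wrong. The ±4-day sampling rule is confined to Week 12, the SAP gives no Week 16 target, and the visit follows each subject's actual last dose. The common midpoint error makes the same slip likely, but does not establish it. Nor does the protocol's minimum of 5 weeks make Day 117 a last permitted day: a minimum sets no upper limit, and a window of 109–117 would itself admit days before that minimum.
- A reader might take 16 of 141 subjects, or 1 in 5 Week 16 samples, as expected losses. The first assumes evenly spread visits and a usable sample from every active subject, although SAP 7.1 removes subjects from the by-visit analyses after discontinuation or a skipped, incorrect or additional dose. The second assumes visits spread evenly over Days 113–117 only; an even spread over ±4 days would give 1 in 9. Both are upper-end illustrations.

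**Conclusion.** The Week 12 discrepancy is real and follows from the SAP alone: the listed window is Days 80–88, while the SAP's own rule, target and day count give Days 81–89. Applied together, the two provisions leave Days 81–88 and lose valid Day 89 samples. For Week 16 the supportable statement is narrower: the limits appear to carry the same one-day offset from nominal Day 113, with no stated target or tolerance to confirm it.

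The issue is minor. The loss is at most about 1 in 9 Week 12 samples under evenly spread visits, and probably far fewer. It affects the descriptive PK summaries and the Week 12 concentration-quartile display. Population PK is to use the available concentrations under a separate analysis plan. The primary, secondary and safety analyses do not use these limits.

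**What to change.** In the list in SAP 7.1, change the Week 12 condition to exclude samples before Day 81 or after Day 89, so that it agrees with the prose rule and Table 2.1.1. For Week 16, state the target day and the tolerance, then set the limits on the same day count: Days 109–117 if ±4 days around Day 113 is intended. If the list was meant to count elapsed days since the first dose, one sentence saying so would serve instead. The cost is a change of up to four numbers, or that one sentence, with the matching lines of code. No data collection changes.

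The limits should be settled before the PK outputs are run, so that no exclusion is chosen with the concentrations in view.

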## 7.2. Immunogenicity

Blood samples will be collected to examine the formation of antibodies to JNJ-64565111 at the specified visits (Day 1, Weeks 2, 6, 12, and 16) as shown in the schedule of events of the protocol. For subjects who discontinue SC study agent administrations, samples will be collected at their 4-week safety follow-up visit.

The data analysis of antibodies to JNJ-64565111 will be summarized if sufficient numbers of subjects are positive for antibodies and will include the following:

- The antibody status (positive, negative) of subjects will be summarized by JNJ-64565111 treatment groups. For subjects who discontinue SC study agent administrations and complete 4-week safety follow-up, a listing of their antibody status will be presented.
- The relationship between antibody to JNJ-64565111 status and efficacy and safety may be assessed at Week 12.
- $\geq 5\%$  and  $\geq 10\%$  weight loss response rates and % weight loss at Week 12 by antibody to JNJ-64565111 status and treatment group
- Injection site reaction by antibody to JNJ-64565111 status and treatment group.
- The relationship between antibody to JNJ-64565111 status at Week 6 and antibody to JNJ-64565111 status at Week 12 will be explored.
- The onset and duration of antibody to JNJ-64565111
- Figure of median serum JNJ-64565111 concentrations by antibody to JNJ-64565111 status.

Other analyses may be performed to verify the stability of antibodies to JNJ-64565111 and/or further characterize the immunogenicity of JNJ-64565111.

### **7.3. Pharmacokinetic/Pharmacodynamic Relationships**

The relationship between serum JNJ-64565111 concentrations and % weight loss may be explored and results will be reported in an independent technical report.

## ATTACHMENTS

### ATTACHMENT 1 CLINICAL LABORATORY TESTS

Blood samples for serum chemistry and hematology, and urine samples for urinalysis will be collected at timepoints specified in the Time and Events Schedule. The investigator must review the laboratory report, document this review, and record any clinically relevant changes occurring during the study in the Adverse Event section of the eCRF and take appropriate action (eg, repeating abnormal laboratory result or further evaluation as considered clinically appropriate). The following tests will be performed by the central laboratory.

- Hematology Panel
  - hemoglobin
  - hematocrit
  - red blood cell (RBC) count
  - white blood cell count with differential
  - platelet count
- Serum Chemistry Panel
  - sodium
  - potassium
  - magnesium
  - chloride
  - bicarbonate
  - uric acid
  - blood urea nitrogen
  - creatinine
  - aspartate aminotransferase
  - alanine aminotransferase
  - gamma-glutamyltransferase
  - total bilirubin
  - alkaline phosphatase
  - creatine phosphokinase
  - lactic acid dehydrogenase
  - amylase
  - lipase
  - calcium
  - phosphate
  - albumin
  - total protein
- Serum  $\beta$ -hydroxybutyrate
- Serum calcitonin
- Fasting insulin\*
- Follicle-stimulating hormone only for women >45 years of age with amenorrhea for at least 6 months and <18 months prior to screening
- Fasting serum lipid profile (triglycerides, LDL-C, HDL-C, total cholesterol) \*
- HbA1c
- Fasting plasma glucose\*
- Urinalysis
  - Dipstick** done at central laboratory
    - specific gravity
    - protein
    - ketones
    - urobilinogen
    - leukocyte esterase
    - pH
    - blood
    - bilirubin
    - nitrite
  - If dipstick result is abnormal, microscopic examination will be performed.
- Serum ( $\beta$ -human chorionic gonadotropin [ $\beta$ -hCG] pregnancy testing will be conducted for all women of childbearing potential (ie, unless they are permanently sterilized or unless there is a documented history of their postmenopausal status) at the screening and Week 12/EOT visits.

Additional serum or urine pregnancy tests may be performed throughout the study in sufficient number, as determined necessary by the investigator, or required by local regulation, to establish the absence of pregnancy during the study.

\* Subjects must be fasting for at least 8 hours before blood sample collections.

### Estimated Glomerular Filtration Rate (eGFR)

- The estimated glomerular filtration rate (eGFR) will be reported according to the Chronic Kidney Disease Epidemiology Collaboration (CKD-EPI) equation\*\* at study visits when serum creatinine is measured. The CKD-EPI equation based on serum creatinine, age, sex, and race for adults age  $\geq 18$  years expressed as a single equation is:

#### CKD-EPI Formula (for $S_{Cr}$ expressed in mg/dL)

$$eGFR = 141 \times \min(S_{Cr} / \kappa, 1)^{\alpha} \times \max(S_{Cr} / \kappa, 1)^{-1.209} \times 0.993^{Age} \times 1.018 \text{ [if female]} \times 1.159 \text{ [if black]}$$

$\kappa = 0.7$  for females

$\kappa = 0.9$  for males

$\alpha = -0.329$  for females

$\alpha = -0.411$  for males

min = the minimum of  $S_{Cr}/\kappa$  or 1 max = the maximum of  $S_{Cr}/\kappa$  or 1

#### CKD-EPI Formula (for $S_{Cr}$ expressed in $\mu\text{mol/L}$ )

$$eGFR = 141 \times \min(S_{Cr} / \kappa, 1)^{\alpha} \times \max(S_{Cr} / \kappa, 1)^{-1.209} \times 0.993^{Age} \times 1.018 \text{ [if female]} \times 1.159 \text{ [if black]}$$

$\kappa = 61.9$  for females

$\kappa = 79.6$  for males

$\alpha = -0.329$  for females

$\alpha = -0.411$  for males

min = the minimum of  $S_{Cr}/\kappa$  or 1 max = the maximum of  $S_{Cr}/\kappa$  or 1

## ATTACHMENT 2 PRE-DEFINED LIMIT OF CHANGE (PDL) CRITERIA FOR LABORATORY TESTS

Laboratory Test	Parameter for ANY value and LAST value
CHEMISTRY	
Albumin	Composite: <LLN and >25% decrease from BL
ALT	Absolute Value: >3X ULN
	Absolute Value: >5X ULN
	Absolute Value: >8X ULN
AST	Absolute Value: >3X ULN
	Absolute Value: >5X ULN
	Absolute Value: >8X ULN
ALT >3X ULN and Tbili >2X ULN	Composite: ALT >3X ULN and Tbili >2X ULN [with the Tbili elevation >2 X ULN within 30 days of the ALT elevation >3x ULN]
AST >3X ULN and Tbili >2X ULN	Composite: AST >3X ULN and Tbili >2X ULN [with the Tbili elevation >2 X ULN within 30 days of the AST elevation >3x ULN]
Amylase	Absolute Value: >2X ULN
	Absolute Value: >3X ULN
	Absolute Value: >5X ULN
Beta-Hydroxybutyrate	Absolute value > 20.822 mg/dL (>2.0 mmol/L)
Bilirubin	Composite: >ULN and > 25% increase from BL
	Absolute Value: >2XULN
Bicarbonate	Absolute Value: <16 mEq/L
Calcitonin	Absolute Value: >20 ng/L (>5.85 pmol/L)
	Absolute Value: >50 ng/L (>14.63 pmol/L)
	Absolute Value: >100 ng/L (>29.26 pmol/L)
Calcium	Composite: >ULN and >10 % increase from BL
Creatinine Kinase	Absolute Value: >1000 U/L
eGFR	Composite: < 80 and decrease >30% from BL
	Change: decrease >50% from BL
Lipase	Absolute Value: >2X ULN
	Absolute Value: >3X ULN
	Absolute Value: >5X ULN
Magnesium	Composite: <LLN and >25% decrease from BL
	Composite: >ULN and >25% increase from BL
Phosphorus	Composite: <LLN and >25% decrease from BL
	Composite: >ULN and >25% increase from BL
Potassium	Composite: <LLN and >15% decrease from BL
	Composite: >ULN and >15% increase from BL
Sodium	Composite: <LLN and decrease >5 mEq/L or more from BL
	Composite: >ULN and increase >5 mEq/L or more from BL
	Absolute Value: <125 mEq/L
Uric Acid	Composite: <LLN and >25% decrease from BL
HEMATOLOGY	
Hemoglobin	Change: ≥2 g/dl decrease from BL
	Change: ≥2 g/dL increase from BL
Platelets	Composite: >ULN and increase >25% from BL
White Blood Count	Composite: < LLN and >25% decrease from BL
	Composite: > ULN and >50 % increase from BL
VITAL SIGNS	
Pulse Rate	Absolute Value: ≤50 beats per minute
	Absolute Value: ≥90, ≥100 beats per minute
	Changes from baseline >30 bpm, >50 bpm
	Absolute value ≥120 bpm and >30 bpm increase from baseline
	Absolute value ≤50 bpm and >20 bpm decrease from baseline
	Decreases from baseline >5, >10, >15, >20 bpm at consecutive visits
Systolic Blood Pressure	Increases from baseline >5, >10, >15, >20 bpm at consecutive visits
	Composite: ≥20 mm Hg decrease from BL and ≤90 mm Hg
	Composite: ≥20 mm Hg increase from BL and ≥160 mm Hg
	Composite: ≥30 mm Hg decrease from BL and ≤90 mm Hg
	Composite: ≥30 mm Hg increase from BL and ≥160 mm Hg

Laboratory Test	Parameter for ANY value and LAST value
	Decreases from baseline >5, >10, >15, >20, >25, >30 mmHg at consecutive visits
	Increases from baseline >5, >10, >15, >20, >25, >30 mmHg at consecutive visits
Diastolic Blood Pressure	Composite: $\geq 15$ mm Hg decrease from BL and $\leq 50$ mm HG
	Composite: $\geq 15$ mm Hg increase from BL and $\geq 100$ mm Hg
	Composite: $\geq 20$ mm Hg decrease from BL and $\leq 50$ mm HG
	Composite: $\geq 20$ mm Hg increase from BL and $\geq 100$ mm Hg
	Decreases from baseline >5, >10, >15, >20, >25, >30 mmHg at consecutive visits
	Increases from baseline >5, >10, >15, >20, >25, >30 mmHg at consecutive visits

**ATTACHMENT 3 ADVERSE EVENTS OF SPECIAL INTEREST**

In order to support the additional assessment of particular categories of adverse events of interest, a list of selected preferred or high-level terms have been created. A blinded review prior to database lock was to be performed to assure that no reported term suggestive of the AE of interest was omitted. AEs of interest include:

- Vomiting
- Diarrhea
- Nausea
- Pancreatic events
- Injection site reactions

The list of preferred and high-level terms for the pre-specified adverse events is provided in EDMS-ERI-181673715.
